Title: FitEx for Endometrial Cancer Survivors: Initial Efficacy

NCT trial number: NCT05737745

November 22, 2024

Study Protocol:

Overview:

This study targets 30 endometrial cancer survivors (ECS) and 2-5 support team members per ECS enrolled in intervention groups. We will use a 3-group design [FitEx (intervention 1) versus FitEx+yoga (intervention 2) versus standard-of-care (control)] with 3 assessments (pre, post [after 8-week program], and follow-up [6-month]). All participants will be given the option to receive a Fitbit Charge 5™ to objectively measure moderate-vigorous physical activity. ECS randomized to either intervention arm will participate in the 8-week FitEx program with their support team members which includes goal setting, self-monitoring, and weekly 30-minute synchronous sessions via Zoom. ECS in the control group will receive a one-time educational newsletter and will not recruit support team members. This protocol will be completed twice, once in 2023 and once in 2024.

OBJECTIVES:

- Aim 1: Among ECS, compare changes in objective MVPA between intervention groups and usual care (FitEx vs. control and FitEx+yoga vs. control) at 8 weeks.
- Aim 2: Among ECS, compare secondary efficacy outcomes and maintenance.
 - Aim 2a: Examine changes in secondary efficacy outcomes [e.g., quality of life (QOL), self-compassion, flourishing, self-efficacy, social support, habituation of exercise, and fruit/vegetable consumption] between intervention and usual care conditions (FitEx versus control and FitEx+yoga versus control) at 8 weeks.
 - Aim 2b: Explore maintenance of MPVA and secondary outcomes between intervention versus usual care (FitEx vs. control and FitEx+yoga vs. control) at 6 months.
- Aim 3: Among support team members, compare changes in MVPA and secondary outcomes (listed above) between intervention groups (FitEx vs. FitEx+yoga) at 8 weeks and 6 months.

RECRUITMENT:

Eligible ECS will be recruited via word-of-mouth, emails, phone calls, and flyers. An informational video on the research project will also be used for recruitment purposes (e.g., linked in emails). The first person to contact a potential participant will always be a Carilion Clinic affiliate on this research study such as [name] or gynecologic oncology clinicians and staff or a clinical research coordinator. The person contacting the participant afterward may be any IRB-approved research personnel on this study. Carilion Clinic affiliates may CC other research study personnel onto email correspondence or reference other research study personnel on phone calls so that other research study personnel may take over the screening or consenting process after the first instance of contact.

ECS who are randomized in either of the intervention groups may recruit up to 5 friends, family members, loved ones, or any support system members to join them as “support team members” within the study. ECS in the intervention groups will identify individuals they wish to be on their intervention team and share relevant contact information (phone number and/or email address of the potential support team members). ECS will be instructed to obtain verbal confirmation of interest from potential support team members before sharing information with research study personnel (ECS confirmation of support team member verbalizing interest in being contacted about the study will be tracked in REDCap). Research study personnel will then contact potential support team members to describe that they received their contact information from the enrolled ECS and to discuss the study and enrollment.

Recruitment will be limited to 3 phone calls and 2 email attempts per participant.

SCREENING & CONSENT

If an ECS is interested in participating, research study personnel will conduct a screening assessment and informed consent process either in-person or virtually. If conducted in-person, the informed consent process documents will be stored in the study coordinator’s office at Carilion Clinic. If conducted virtually, the informed consent process will be documented within REDCap. Participants may be consented on REDCap either over the phone or via teleconference depending on their preference. Consents conducted via teleconference will use secure, password protected Microsoft Teams or WebEx platforms. Zoom will not be used to consent participants. Support team members will undergo the same consent process as ECS after follow-up call and screening. All participants will be provided ample time to decide if they would like to join the study. There will be multiple opportunities for the participant to opt out before enrollment. Prior to consent, all potential participants will be sent a copy of the consent form for their review. A phone call or secure, web-based teleconference will be scheduled for interested participants to fill out the econsent via REDCap.

RANDOMIZATION & GROUPS

Each ECS who enrolls in the study will be randomized into one of three groups:

1. Standard-of-care (control)
2. FitEx intervention (FitEx-ECS)
3. FitEx intervention with integrated yoga principles (FitEx-ECS+yoga)

Overall, this study targets 10 ECS per group (30 total ECS) with 2-5 support team members per ECS in each intervention group (approximately 30 total support team members in each intervention group) yearly, for 2 years (90 participants per year, 180 participants total). All participants will be given the option to receive a Fitbit Charge 5™ to objectively measure moderate-vigorous physical activity.

Control Group:

ECS in the control group will be given the option to receive a Fitbit and will be sent a one-time educational newsletter about survivorship PA and nutrition recommendations. Control group participants will fill out all questionnaires at baseline, post, and 6-months follow up. Control

group participants will not recruit support team members, fill out FitEx-specific forms, nor participate in weekly Zoom sessions.

Intervention Groups:

ECS randomized to either intervention arm will participate in the 8-week FitEx program adapted for ECS with their support team members. The FitEx-ECS intervention will entail group dynamics, goal setting, self-monitoring (tracking physical activity and fruit and vegetables intake via the FitEx-ECS portal within Fitabase or the FitEx Individual Log form), and feedback on goal attainment. The FitEx-ECS+yoga intervention will entail postures, breathwork, and mindfulness in addition to group dynamics, goal setting, self-monitoring (tracking physical activity and fruits and vegetables intake via the FitEx-ECS portal within Fitabase), and feedback on goal attainment. Each participant of either intervention group will have the option to receive Fitbit Charge 5TMs, fill out repeated program forms and questionnaires, and read weekly group-specific newsletters. Participants in either intervention will not have to pay any intervention program-related fees.

Additionally, all participants will be asked to report their weight during the baseline, post-program, and 6-month follow up questionnaires packet (see updated questionnaires document). Participants may also choose to report their weight using the FitEx-ECS portal within Fitabase.

Participants from both intervention groups will also be strongly encouraged to attend weekly group-specific 30-minute synchronous Zoom sessions consisting of virtual physical activity and social support with other teams. Topics for both intervention groups are similar, however the FitEx-ECS+yoga group's newsletter and virtual sessions are guided by yoga principles and mindfulness. Participants in the Zoom sessions will be verbally reminded of the audio recording at the beginning of each session. Participants may choose to turn on or off their cameras according to what is most comfortable.

SMS Reminders to Sync:

Participants in all groups with Fitbit devices who have not synced their Fitbit devices after 6 days will receive up to a maximum of two automated SMS-based reminders per week.

- Prompt: "Please open your Fitbit app and sync this past week's activity."

Automated SMS-based prompts will be set up using the FitEx-ECS portal within Fitabase. Fitabase uses Azure Always Encrypted to encrypt phone numbers at rest and in transit to protect participant personal information.

COMPENSATION

After enrollment: All participants will have the option to receive Fitbit Charge 5TMs to track their data over the course of the study and for them to keep after the study. If a participant already owns a Fitbit they wish to use, they will instead be reimbursed \$99 for using their personal Fitbit for the study.

Post-intervention: Upon completion of the post-program exit interviews, participants in the intervention groups will receive \$10.

At 6-months follow-up: Upon completion of both filling out the program survey and wearing their Fitbit for one week at the 6-months follow-up timepoint, all participants (from any of the three groups) will be compensated \$20.

ASSESSMENTS

All participants will be assessed at baseline (week 1), post-program (week 9), and follow-up (6 months).

Pre-program:

At baseline, participants in all three groups will have the option to record Fitbit data for 7 days. Participants in the intervention groups will also be asked to track self-monitored physical activity, track self-monitored fruit and vegetables intake, and fill out the FitEx pre-program form. All participants will receive questionnaires. Questionnaires will be distributed via REDCap at baseline, post, and follow up.

Program:

During the 8-week duration of intervention program, Fitbit data will be collected from all participants in the control, FitEx-ECS, and FitEx-ECS+yoga groups.

In both intervention groups, self-monitored physical activity and fruit and vegetables intake will be tracked with the FitEx-ECS portal within Fitabase or with the FitEx Individual Log (see attached). Intervention group-specific weekly newsletters and Zoom sessions will occur throughout the duration of the 8 weeks. Intervention participants will be verbally reminded of the audio recording at the beginning of each Zoom session.

Additionally, a video of each session's synchronous movement will be recorded by the instructor only so that participants in either intervention group who were unable to attend can participate in the physical movement when their schedule allows.

Post-program:

After the 8-week program, participants in both intervention groups will fill out the FitEx post-program form and participants in all groups will repeat questionnaires, all distributed via REDCap. For both intervention groups, 30- to 45-minute semi-structured interviews will be scheduled and conducted with ECS survivors and support team members (See "Follow Up Materials" attachment for interview guide.)

Questionnaires & surveys:

Questionnaires for intervention groups include: 1. The Stanford Leisure-Time Activity Categorical Item (L-CAT) 2. 6 items from the validated Behavioral Risk Factor Surveillance System survey (BRFSS F/V), 3. Flourishing Index, 4. Yoga Self-Efficacy Scale (YSES), 5. Social Support for Exercise Survey (SSES), 6. Self-Compassion Scale Short Form (SCS-SF), 7. Self-Reported Behavior Automaticity Index (SRBAI), and 8. The Functional Assessment of Cancer Therapy - Endometrial (FACT-En). Additionally, all participants will be asked to report their weight within the questionnaires packet (see updated questionnaires document). All

questionnaires will be electronically facilitated with REDCap. ECS will be sent all questionnaires to fill out. Support team members will be sent all questionnaires to fill out except the FACT-En.

Electronic questionnaires will be sent in an automated email via REDCap up to two times for each timepoint: baseline (week 1), post-program (week 9), and follow-up (6-months)

6-month follow-up:

All participants will be contacted via their preferred method at follow-up (6 months) to schedule a 7-day long follow-up assessment. All participants will be asked to record Fitbit data for the 7-day duration and fill out questionnaires. Participants in the intervention groups will also self-monitor other physical activity, self-monitor fruits and vegetables intake, and the FitEx follow-up program form. Control group participants will be invited to future iterations of the FitEx interventions.

Zoom:

This research study is using Zoom as the virtual web conferencing platform for weekly meetings. The meetings conducted during this study will be recorded by the researcher using the audio and video recording capabilities available in the Zoom videoconferencing platform.

STATISTICAL ASSESSMENT:

Measures

Due to the small sample size and exploratory nature of this pilot study, statistical analyses will be descriptive rather than inferential. However, we will determine if a signal exists between intervention and control groups regarding participants' physical activity using MET (metabolic equivalents) data from Fitbits. Weekly data will be compared at week-8 (intervention conclusion) to baseline. Data is considered appropriate if it was collected from at least 4 days per week. Data from missing days was input at "0". Students T-tests were used to compare means from each intervention group to the control condition for the primary outcome.

Attendance/Retention Measures

Participants who enroll in the study will be asked to attend weekly meetings. The attendance at the meetings will be recorded to assess the percentage of participants who are interested in weekly meetings. The acceptability of FitEx will be assessed in part using meeting attendance. Attendance and retention will be used as measures of intervention acceptability.

The number of support group members who attend each session will also be noted. The ratio of support group members to endometrial cancer survivor participants will also be noted.

We will examine our attrition rate and attendance as noted above. We will also reach out to participants who do not complete our study to determine the reasons for their decisions. Our study will be feasible in its current state if our attrition rate is between 10-27%.

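### Survivors' baseline questionnaires follow randomisation, and apparently follow or overlap support-team recruitment, so baseline social support may already reflect the allocated arm

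*Combined protocol and SAP*

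**What the plan says.** On allocation, RANDOMIZATION & GROUPS says: "Each ECS who enrolls in the study will be randomized into one of three groups". On teams, RECRUITMENT says: "ECS who are randomized in either of the intervention groups may recruit up to 5 friends, family members, loved ones". The survivor first obtains each person's verbal interest; study staff then contact, screen and consent that person. For controls, "group participants will not recruit support team members".

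On timing, ASSESSMENTS says: "All participants will be assessed at baseline (week 1), post-program (week 9), and follow-up (6 months". The questionnaire subsection says: "Electronic questionnaires will be sent in an automated email via REDCap up to two times for each timepoint: baseline (week 1". Supporters are on the same schedule: "Support team members will be sent all questionnaires to fill out except the FACT-En". Baseline tasks already differ by arm: "Participants in the intervention groups will also be asked to track self-monitored physical activity, track self-monitored fruit and vegetables intake".

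The questionnaires include the Social Support for Exercise Survey. Aim 2a compares changes in secondary outcomes, among them "self-efficacy, social support, habituation of exercise, and fruit/vegetable consumption] between intervention and usual care conditions". The STATISTICAL ASSESSMENT section makes the analysis descriptive and names a t-test for the primary outcome only.

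**The concern.** A baseline is safe to subtract when it is measured before the arms have been treated differently. Here it appears to be measured afterwards. A survivor in an intervention arm knows her allocation and may already have asked friends and family to exercise with her, and had them agree. That bears directly on what a survey of social support for exercise is meant to capture. A control survivor does nothing comparable.

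If those early steps move the week-1 score, subtracting it takes part of the intervention's effect out of the Aim 2a contrast. Randomisation does not repair this, because the disturbance arises after it. A descriptive mean change is affected in the same way as a tested one. Social support is the outcome most exposed, because recruiting a team is itself part of the intervention.

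**Working it through.** **Step 1: order of events.**

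| Event | Where stated | Who |
|---|---|---|
| Randomisation on enrolment | RANDOMIZATION & GROUPS | All survivors |
| Approach to supporters, verbal interest obtained | RECRUITMENT | Intervention survivors only |
| Supporters contacted, screened, consented | RECRUITMENT; SCREENING & CONSENT | Supporters |
| Week-1 baseline and questionnaires | ASSESSMENTS | All survivors and supporters |

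*Baseline after allocation* is well supported. Arm-specific baseline tasks are possible only if the arm is known, and no section puts a survivor questionnaire before randomisation.

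*Baseline after or during team recruitment* is an inference. Supporters can have a week-1 baseline only if they have been approached and consented by about then. It assumes that survivors and their supporters share one week 1, which the documents do not say. Week 1 is not defined relative to randomisation, recruitment or the first session.

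**Step 2: effect on the contrast.** The documents give no effect size or SD for social support, so there is no planned figure to reproduce. Let

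- τ = true effect on the week-9 score, intervention minus control;
- f = between-arm difference in expected baseline score caused by allocation and team recruitment, as a share of τ.

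Then:

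- difference in change = τ − fτ = τ(1 − f);
- difference adjusted for baseline with slope b = τ − b·fτ = τ(1 − b·f);
- difference in week-9 scores alone = τ.

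The values of f and b = 0.5 below are assumptions. The plan specifies no baseline-adjusted model; that column is for comparison.

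| f | Change, share of τ | Adjusted (b = 0.5), share of τ | Week 9 only, share of τ |
|---|---|---|---|
| 0 | 1.00 | 1.00 | 1.00 |
| 0.10 | 0.90 | 0.95 | 1.00 |
| 0.25 | 0.75 | 0.875 | 1.00 |
| 0.50 | 0.50 | 0.75 | 1.00 |
| −0.10 | 1.10 | 1.05 | 1.00 |

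The last row covers the opposite case, where intervention survivors rate their baseline support lower and change is overstated.

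**Step 3: size against sampling noise.** Assume the SD of change equals the SD of the score. The standard error of a between-arm difference is then √(2/10) = 0.45 SD with 10 survivors per arm (one yearly cohort) and √(2/20) = 0.32 SD with 20 (two cohorts). With an assumed τ of 0.8 SD, f = 0.10, 0.25 and 0.50 shift the contrast by 0.08, 0.20 and 0.40 SD. Only the last exceeds a standard error, and only at 20 per arm. The shift is systematic, so it does not average out, but the baseline table will be too imprecise to confirm it or rule it out.

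**The case against.** A reader might infer that baseline social support is already post-intervention and that its change is understated. The documents do not support either as fact. They label the assessment as pre-program and leave week 1 undefined. Questionnaires go out by automated email, with no stated order of completion between survivor and supporters. Recruiting supporters is worded as optional for the survivor. The survey's items and recall period are not in the text, so it cannot be shown that agreement obtained before the programme would move the score. Group dynamics and the weekly sessions come later. A survivor who struggles to find helpers, or a control who knows her allocation, could shift the baseline the other way. All of this stands, and it limits the point to a possible bias, probably but not certainly towards attenuation.

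Two further inferences should be resisted. One is a specific percentage loss: any such figure is a ratio of assumed quantities. The other is extension to quality of life, flourishing or diet: the documents suggest no mechanism by which forming a team would shift those scores before the programme.

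It is also fair that this is a secondary outcome in a descriptive pilot, and that the document's date (November 2024) and the 2023 and 2024 cohorts suggest that moving the questionnaires may come too late for most participants. That reduces the weight of the point and makes the reporting remedy the more practical one. It does not remove the point: followed as written, the plan yields an unblinded baseline collected after allocation for a named change outcome.

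**Conclusion.** The concern holds in a limited form. That survivors' questionnaires follow randomisation is well supported; that they follow or overlap team recruitment is a reasonable inference resting on the shared week-1 baseline. Baseline social support may therefore already reflect allocation and team formation in the two intervention arms, and the change contrast would show (1 − f) of the true effect. No value or sign of f can be derived from the documents. Attenuation is more likely if being joined by a team raises perceived support before week 1. The consequence is confined to a descriptively analysed secondary outcome; nothing here bears on the Fitbit primary outcome. The change is worth making because it is cheap and removes the ambiguity by design.

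**What to change.** **Future enrolment.** Send each survivor's baseline REDCap packet at consent, and require completion before she is randomised and before any supporter is approached. Supporters keep their week-1 baseline. Define week 1 relative to randomisation, team recruitment and the first session. This makes f = 0 by design. The cost is moving an automated email, a possible wait for the packet before randomisation, and a somewhat older questionnaire baseline at programme start.

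**Survivors already enrolled under the current order.** Report baseline social support by arm, give the week-9 between-arm difference without baseline subtraction beside the change, and state that baseline was collected after allocation. This needs no new data, only an extra summary. The week-9 difference is free of this bias but may be noisier: with equal SDs σ at both visits and correlation ρ, change has variance 2(1 − ρ)σ², which is below σ² when ρ exceeds 0.5. That is why both should be shown.

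### Only the intervention arms log activity and diet in the baseline and 6-month assessment weeks, so the survivors' change-from-baseline contrast with control may carry a bias of unknown size

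*Combined protocol and SAP*

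**What the plan says.** The Pre-program part of ASSESSMENTS offers every group a 7-day Fitbit recording at baseline and then adds, for two of the three groups: "Participants in the intervention groups will also be asked to track self-monitored physical activity, track self-monitored fruit and vegetables intake". The same sentence gives those groups the FitEx pre-program form. Under Control Group, the plan says that control "group participants will not recruit support team members, fill out FitEx-specific forms, nor participate in weekly Zoom sessions".

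The logging is not described only as measurement. Under Intervention Groups: "The FitEx-ECS intervention will entail group dynamics, goal setting, self-monitoring". The yoga arm has the same component.

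The baseline week is the reference for the main comparison. Aim 1 is to "compare changes in objective MVPA between intervention groups and usual care (FitEx vs. control and FitEx+yoga vs. control) at 8 weeks", and the Measures section sets week 8 against baseline. Aim 2b is to "Explore maintenance of MPVA and secondary outcomes between intervention versus usual care". The 6-month follow-up section again asks only the intervention groups to self-monitor and to complete a FitEx form in the 7-day assessment.

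On timing, the plan randomizes each ECS who enrolls and states: "All participants will be assessed at baseline (week 1), post-program (week 9), and follow-up (6 months"). No sentence gives the order of allocation and baseline. Control participants "will be sent a one-time educational newsletter about survivorship PA and nutrition recommendations", with no date given.

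**The concern.** A change score is only as good as its reference week. If a component of the intervention is already running in that week in two arms and not in the third, any response to it raises or lowers the reference in those arms only. In the week-8 contrast the effect of logging belongs to the intervention. In the baseline week it does not, and there it is subtracted from the estimated effect.

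Fitbit wear, itself a form of self-monitoring, is offered to all arms. What differs is therefore narrower: the extra reactivity to logging, plus any reaction to knowing the arm. Logging may raise activity, so the likeliest result is a contrast pulled toward no effect, in a pilot whose stated purpose is to look for a signal against control. An early control newsletter could offset this.

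**Working it through.** **Is the arm known at baseline?** Baseline tasks are assigned by group, and a group-specific task cannot be given before the group is known. Randomization is tied to enrollment, and nothing places baseline before it. Post-allocation timing is thus a fair inference, though not a stated fact.

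**Which outcomes?**
- MVPA comes from the Fitbit in all arms, so a shift in behaviour during the logged week would appear in it.
- Fruit and vegetable intake is measured by BRFSS items in a questionnaire that all ECS complete. It is affected only if that questionnaire is answered after logging starts or after the arm is known. The plan gives no order.
- Aim 3 compares two arms that both log, so it is largely unaffected.

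**Inputs.** From the plan: 10 ECS per group per year for 2 years, so n = 10 per arm in one year and 20 pooled. Its enrollment target reproduces: (3 × 10 + 2 × 30) × 2 = 180. The plan gives no effect size, SD or reactivity, so every other input is assumed: a true week-8 difference D = 60 min/week, a true 6-month difference D6 = 30 min/week, net shifts (intervention minus control) s0 at baseline and s6 in the 6-month week, and a baseline to week-8 correlation r = 0.7.

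**Week 8.** Change-score contrast = D − s0. Contrast of week-8 means = D.

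| s0 | Change score | Week-8 means |
|---|---|---|
| −6 | 66 | 60 |
| 0 | 60 | 60 |
| 6 | 54 | 60 |
| 15 | 45 | 60 |

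**Six months.** Change-score contrast as planned = D6 + s6 − s0. If only the baseline were aligned, it would be D6 + s6.

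| s0 | s6 | As planned | Baseline aligned only | Both weeks aligned |
|---|---|---|---|---|
| 6 | 6 | 30 | 36 | 30 |
| 15 | 15 | 30 | 45 | 30 |
| 15 | 6 | 21 | 36 | 30 |
| 6 | 15 | 39 | 45 | 30 |

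The two shifts cancel only if equal, and correcting the baseline alone would expose s6. Both weeks need the same treatment.

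**Could a week-8-means analysis reveal the bias afterwards?** The two contrasts differ by exactly the observed baseline difference between arms. By chance alone that difference has standard error √(2/n) SD: √(2/20) = 0.32 and √(2/10) = 0.45. If 60 min/week is taken as 0.8 SD (assumed), then SD = 60/0.8 = 75, and shifts of 6 and 15 are 0.08 and 0.20 SD. Even the larger is below one standard error (0.20/0.32 = 0.63 at n = 20; 0.20/0.45 = 0.44 at n = 10). Fitbit use is optional, so the analysable n may be smaller still.

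**Would week-8 means be the better estimate?** In SD units the variance is 2/n for week-8 means and 4(1 − r)/n for change scores. The standard-error ratio at r = 0.7 is 1/√(2 × 0.3) = 1.29. Mean squared errors are equal at a shift of √(2/n − 4(1 − r)/n) = √(0.8/n), which is 0.20 SD at n = 20 and 0.28 SD at n = 10. On these assumptions the 15-minute shift only breaks even at n = 20, and neither shift reaches break-even at n = 10.

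**The case against.** The strongest reply is that nothing in the documents shows an effect of this logging. All arms may wear the device that measures the outcome, the log appears under a pre-program assessment heading, and goal setting, feedback, newsletters and Zoom sessions are not placed in that week. The content of the pre-program form is not given. The t-test sentence speaks of comparing means, and if these are week-8 means the bias is absent. The analysis is declared descriptive. The program was to run in 2023 and 2024 and the document is dated November 2024, so the baselines have probably been collected.

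Most of this stands and limits the point. It does not remove it: the tasks are unequal in the reference week, the plan itself calls the logging part of the intervention, and Aim 1 is framed as change.

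A reader might go further in three ways that the documents do not support.
- **That support-team recruitment proves allocation came before the ECS baseline.** The plan says that "ECS who are randomized in either of the intervention groups may recruit up to 5 friends, family members, loved ones", but the support members' baseline need not fall in the same week as the survivor's. The group-specific tasks are the better evidence.
- **That the intervention as a whole starts in the baseline week**, since baseline is labelled week 1. Only the logging and the form are placed there, under a pre-program heading.
- **That all secondary outcomes are distorted.** No route from logging to outcomes such as flourishing is shown.

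**Conclusion.** The point holds in a limited form and is minor. The unequal tasks in both 7-day assessment weeks are explicit. That the arm is known at baseline is inferred. The consequence is a possible bias in the ECS change contrast with control for MVPA, and conditionally for fruit and vegetable intake. Toward no effect is the likeliest direction.

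It would be tempting to conclude that the trial understates the effect by a given amount. The documents do not support that: the minutes shown are assumptions, a zero or reversed shift is possible, and the undated control newsletter could work the other way. Nor would agreement or disagreement between change scores and week-8 means settle the matter at 10 to 20 ECS per arm.

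**What to change.** For later iterations:
1. Complete the 7-day Fitbit baseline and the baseline questionnaires for ECS before the arm is disclosed, with identical tasks in all arms. Start FitEx logs and the pre-program form, and send the control newsletter, only afterwards.
2. Keep tasks identical across arms in the 7-day 6-month assessment, and place any intervention-only log or form after it.
3. State that the Aim 1 t-test compares change from this baseline.

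For cohorts already collected, report the order of allocation, first device day, first log and newsletter, and name the unequal baseline tasks as a limitation. Do not present a week-8-means comparison as a test for this bias.

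**Cost.** No added visits or measurements. Disclosure and team formation move about one week later. The ECS baseline then ends before the support-team baseline, so controls should keep the same gap. Intervention ECS have a slightly longer 6-month follow-up. For completed cohorts the cost is a few dates and one limitation sentence.
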